### **Data Analysis**

**Aim 1-** Statistical considerations: Power and sample size: We wish to have adequate power to detect a difference of ~20% in calories purchased between the groups. Data from studies on adolescents' snack choices indicated an average of 400–600 calories. Thus, we wish to detect a between-group difference of ~100 calories. Estimates of standard deviation of food choices vary widely. Most estimates are 100–300 calories, but to be conservative, and because we do not have direct data on purchases in an online survey, we assume a standard deviation of 400calories. Accounting for participants who fail the attention check item, and using a two-sided Type I error rate of 0.017to control the experiment-wise error rate to 0.05, a final sample size of 1,252 participants (100 pre-test participants that will not be part of the final sample, plus 288 per group in each of the four conditions =

<sup>30 Harris JL, Bargh JA, Brownell KD. Priming effects of television food advertising on eating behavior. *Health Psychol.* 2009;28(4):404-413.

<sup>31 Dias M, Agante L. Can advergames boost children's healthier eating habits? A comparison between healthy and non-healthy food. *J Consumer Behav*. 2011;10(3):152-160.

<sup>32 Harris JL, Speers SE, Schwartz MB, Brownell KD. US Food Company Branded Advergames on the Internet: Children's exposure and effects on snack consumption. *Journal of Children and Media*. 2012;6(1):51-68.

1,252 total participants)provides 80% power to detect a difference of 80 calories between the groups who see racially congruent vs. racially incongruent ads. This sample size also provides 80% power to detect a difference of 113 calories between White adolescents who see racially congruent ads and Black adolescents who see racially congruent ads. Secondary outcomes: This sample size provides 80% power to detect an effect size of 0.2 standard deviation (SD)between outcomes. Analytic plans: Descriptive analyses: All data will be summarized prior to analysis, using means, medians, ranges, and standard deviations for continuous variables and frequencies for categorical variables. BMI-z scores, which a readjusted for age and sex, will be calculated using Centers for Disease Control growth charts. Participants who fail our data integrity check questions will be excluded. This is expected to be ~9% of participants based on our pilot studies and previous work with adolescents.We will assess balance by randomization status with respect to demographic and behavioral factors. Adjustment of primary analyses will be undertaken to accommodate any imbalances

Analysis of primary outcome: Linear regression will be used to evaluate whether the number of calories purchased by the adolescents who viewed racially congruent ads differs from those who viewed racially incongruent ads. If the calorie count data are skewed, a suitable transformation (e.g., log) will be applied to improve the approximation of normality. To evaluate our hypothesis that Black adolescents—compared to White adolescents—will purchase more calories after viewing racially congruent ads, an additional model will also include a term for participant race, as well as an interaction term between participant race and ad congruence to determine if there is a differential association. We will also run all models controlling for eating restraint and presence of eating disorders symptoms to examine if those factors affect the number of calories purchased by adolescents. Analyses of secondary outcomes: We will use linear regression models that include participant race, racial congruence, and the interaction of the two as predictors; emotional responses to the ads and time spent viewing ads will be our outcomes. To investigate affective responses to the ad as a potential mediator for the relationship between the type of ad viewed and calories purchased, an additional model will include participant race, racial congruence of the ads, and an interaction term, as well as affective responses to the ads as predictors of calories purchased. We Will assess whether associations between calories purchased and the racial congruence term and the interaction between racial congruence and participant race term are weakened by the addition of affective response to the model. We will use the Bonferroni-holm procedure to correct for multiple comparison

**Aim 2-** Statistical considerations: Power and sample size: We wish to have adequate power to detect a difference of ~20% in calories purchased between the conditions. As in Aim 1, we use data from studies on adolescents' snack selections to inform power calculations. Using a two-sided Type I error rate of 0.017 to control the experiment-wise error rate at 0.05, assuming a SD of 400 calories, and accounting for some participants to fail an attention check item, a sample size of 1,200 participants (600 in each of two conditions = 1,200 total, not including the 100 pretest participants) provides 80% power to detect a difference of 78 calories between teens viewing ads with many "likes" vs. few "likes." This sample size also provides 80% power to detect a difference of 110 calories between White adolescents and Black adolescents who see ads with many "likes." Secondary outcomes: This

<sup>33 Bragg MA, Miller AN, Kalkstein DA, Elbel B, Roberto CA. Evaluating the influence of racially targeted food and beverage advertisements on Black and White adolescents' perceptions and preferences. *Appetite*. 2019;140:41-49.

sample size provides 80% power to detect an effect size of 0.2 SD between conditions. Analytic plans: Descriptive analyses: Data will be summarized as described in Aim 1. We will assess balance by randomization status with respect to demographic and behavioral factors. Adjustment of primary analyses will be undertaken to accommodate any imbalances. Primary outcome: Linear regression will be used to evaluate differences in the mean calories purchased between conditions, with appropriate transformations to improve the approximation of normality if necessary. To explore whether the effect of many vs. few "likes" varies by race, we will include participant race as a main effect, as well as an interaction term between race and condition. We will also use linear regression to adjust for demographic and behavioral characteristics to investigate how these factors relate to responsiveness to ads. We will also conduct sensitivity analyses to control for the presence of eating disorder symptoms measured at the end of the study. Finally, participants who fail our data integrity check questions will be excluded. This is expected to be <9% of participants based on our pilot studies. Secondary outcomes: We will use linear regression models to assess the relationships between the number of "likes" on the ad and cognitive and emotional responses as well as time spent viewing ads. We will evaluate whether the association between the number of "likes" and calories consumed is moderated by affective responses to the model. The Bonferroni-Holm procedure will be used to correct for multiple comparisons.

**Aim 3-** Statistical considerations: Power and sample size: We based our sample size on the expectation of a racial congruence effect that is small in size for White adolescents (0.2) and larger for Black adolescents (0.3). West our final sample size with the requirement of 80% power to detect the smallest correlation coefficient (at least 0.2) within each group (i.e., 200 Black and 200 White adolescents provide adequate power). Analytic plans: We will follow data cleaning procedures for eyetracking data established by our collaborator [name] for handling data loss or calibration issues.The sampling rate—the proportion of time eyes are directed at the screen—must equal 80% or higher. Participants with <20% sampling rate will be eliminated (typically <5% of participants). Sampling Rates can be low because some rare types of cornea refractions and contact lens types impair the reflection of light the system measures. To account for nonindependence in consumption across blocks, we will conduct analyses using the MIXED procedure in SPSS, and calculate degrees of freedom using a Satterthwaite correction to predict consumption as a function of ad type within blocks 1–4 and separately blocks 5–8. We will include the random intercept of participants, the random intercept of block order, and the random slope of block order to account for linear changes in consumption over time. We will use linear regression to predict calorie intake from visual attention to race-relevant ad features, product, and "likes" for Black and White adolescents

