### **Purpose of the Study and Background**

### Purpose of the Study

Poor diet and excess weight during adolescence predicts excess weight and diet-related cancers during adulthood, yet there is little research on the risk factors that contribute to weight gain among adolescents. The National Academy of Medicine identifies exposure to food advertisements (ads)as a major predictor of poor diet among children (<12 years of age) because studies have shown that children who are exposed to food ads consume more calories than children who are exposed to nonfood ads. The few food ad studies that have included adolescents (13-17 years of age) found associations between self-reported exposure to television (TV)food ads and poor diet, but we do not know which mechanisms explain this relationship. It is also well established that food companies promote their least healthy products to Black consumers more than White consumers and perceive Black youth as trendsetters. But it is not known whether seeing racially congruent ads (i.e., the person in the ad and the viewer are the same race) places Black adolescents at higher risk of poor diet relative to Whites. Finally, most food ad research is based on TV ads, but food companies are increasingly targeting adolescents on social media. The overall objective of our three studies is to identify the extent to which exposure to Facebook food ads increases the number of calories purchased and consumed by Black and White adolescents. Guided by strong preliminary data, we will test three aims: 1)To evaluate the extent to which exposure to racially congruent vs. incongruent Facebook food ads causes Black vs. White adolescents to purchase more calories for a snack;2)To determine the extent to which exposure to many vs. few "likes" on Facebook food ads causes Black and White adolescents to purchase more calories for a snack; and 3)To test the degree to which visual attention to unhealthy foods, racially congruent people, and/or "likes" in Facebook ads explains the relationship between ad exposure and calorie intake.

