# **Study Design**

The overall objective is to determine the extent to which racially congruent Facebook food ads influence adolescents' food purchases and actual caloric intake. We will accomplish these objectives by conducting three randomized controlled trials (RCTs). The first two aims trials will involve 15minute online surveys in which participants (Black and White adolescents) will rate ads then complete a "food purchasing" task through a virtual vending machine. The third trial will involve an in-person, hour long lab study where participants will be shown ads while investigators covertly monitor their eye movements. The first RCT will answer the research question "Does exposure to racially congruent vs. incongruent Facebook ads for unhealthy foods cause Black (vs. White) adolescents to purchase snacks with more calories?". The second RCT will answer: "Does exposure to many "likes" (vs. few "likes") on Facebook ads for unhealthy foods lead to even higher calorie purchases for both Black and White adolescents?". Lastly, the hour-long study will answer the question: "To what extent does the visual attention to foods vs. people vs. "likes" in ads predict adolescents' caloric intake?" (Aim 3). For the first two online survey trials, we will measure the average calories purchased for a snack and for the last trial we will measure the average calories consumed.

<sup>19 Harris JL, Schwartz MB, LoDolce M, et al. Sugary drink FACTS 2014: Some progress but much room for improvement in marketing to youth. *Rudd Center for Food Policy and Obesity: New Haven, CT*. 2014.

<sup>20 Harris JL, Schwartz MB, Munsell CR, et al. Fast food FACTS 2013: Measuring progress in nutrition and marketing to children and teens. *Yale Rudd Center for Food Policy and Obesity*. 2013.

<sup>21 Grier SA, Kumanyika S. Targeted marketing and public health. Annu Rev Public Health. 2010;31:349-369.

<sup>22 Harris JL, Shehan C, Gross R, et al. *Food Advertising Targeted to Hispanic and Black Youth: Contributing to Health Disparities*. Rudd Center for Food Policy & Obesity; 2015.

<sup>23 Story M, French S. Food Advertising and Marketing Directed at Children and Adolescents in the US. *Int J Behav Nutr Phys Act*. 2004;1(1):3.

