### Racial and Ethnic Origin

We will recruit 3,032 adolescents that identify as only non-Latino White or only Black/African American. The purpose being that targeted ads usually appeal to Black youth in particular. This marketing tactic is a potent one worth further investigation since most of the targeted ads are for unhealthy foods. And black adolescents experience higher rates of obesity and report higher social media use than their peers. We will use the White participants as a comparison group since they are featured in most ads and are, therefore, unlikely to experience heightened effects from racially targeted ads. There are plans to study other racial/ethnic groups in future research, but we would not be adequately powered in this proposal to understand the effects for each racial/ethnic group.

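### Aim 1: the 113-calorie power figure is for Black versus White adolescents within the congruent arm; the planned race-by-congruence interaction is detectable only at about 160 calories at SD 400

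*Combined protocol and SAP*

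**What the plan says.** The Aim 1 power statement (Data Analysis) gives two calorie figures at 80% power. One is 80 calories for congruent versus incongruent ads. The other is "80% power to detect a difference of 113 calories between White adolescents who see racially congruent ads and Black adolescents who see racially congruent ads". The 0.2 SD statements, there and under Number of Subjects, concern conditions or secondary outcomes.

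The analysis of the primary outcome takes up the race hypothesis in an additional model containing participant race, "as well as an interaction term between participant race and ad congruence to determine if there is a differential association". The mediation analysis uses the same term for calories purchased, asking whether the congruence association and "the interaction between racial congruence and participant race term are weakened by the addition of affective response to the model".

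Three other sections frame the question as one of differential response:
- Purpose of the Study: whether exposure to "racially congruent vs. incongruent Facebook food ads causes Black vs. White adolescents to purchase more calories for a snack".
- Study Design: "Does exposure to racially congruent vs. incongruent Facebook ads for unhealthy foods cause Black (vs. White) adolescents to purchase snacks with more calories".
- Racial and Ethnic Origin: White participants are a comparison group, "unlikely to experience heightened effects from racially targeted ads".

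On effect size and variability the plan says "Thus, we wish to detect a between-group difference of ~100 calories". On the SD it says "Most estimates are 100–300 calories, but to be conservative", and it then assumes 400.

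**The concern.** The power figure and the planned test belong to different contrasts. The 113 calories compare two cells: Black and White adolescents who both saw congruent ads. The interaction compares the congruence effect in Black adolescents with the congruence effect in White adolescents, which uses four cells and has twice the variance.

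The two contrasts also answer different questions. Race is not randomised. As an illustration, suppose Black adolescents bought 113 calories more than White adolescents whichever ads they saw. The within-arm contrast would be 113 and the interaction 113 − 113 = 0. Conversely, the within-arm contrast could be zero while congruence acted differently in the two groups.

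A reader looking for the sensitivity of the race test finds only 113 calories. If the interaction is then not significant, that figure invites the conclusion that Black and White adolescents respond alike, although at the planning SD the study would often miss an interaction of that size.

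**Working it through.** **Inputs, all from Data Analysis, Aim 1.** SD 400 calories; two-sided alpha 0.017; 80% power; 288 per group in four groups, with the 100 pre-test participants left out; about 9% excluded for failed integrity checks. Analysable per cell: 288 × 0.91 = 262.

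**Layout.** The four groups are read as race (2) by congruence (2) with equal cells. The plan does not spell this out, but both of its figures reproduce on that reading.

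**Multiplier.** z(0.9915) + z(0.80) = 2.387 + 0.842 = 3.228.

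**Step 1: reproduce the plan's figures.** Detectable difference between two groups = 3.228 × SD × √(2/n).
- Congruent versus incongruent, n = 524 per arm: 3.228 × 400 × √(2/524) = 79.8 (stated: 80).
- Black versus White within the congruent arm, n = 262: 3.228 × 400 × √(2/262) = 112.8 (stated: 113).

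Without exclusions these would be 76.1 and 107.6, so the plan's figures do include the 9% loss.

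**Step 2: the interaction on the same basis.** Its standard error is SD × √(4/n) = 400 × √(4/262) = 49.4. Detectable size = 3.228 × 49.4 = 159.6 calories. That is √2 times the within-arm figure and twice the main-effect figure. With no exclusions (n = 288) it is 152.2.

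**Step 3: range over the SD (262 per cell).**

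| SD | Detectable at alpha 0.017 | Detectable at alpha 0.05 | Power at 100 (alpha 0.017) | Power at 113 (alpha 0.017) | 95% half-width |
|---|---|---|---|---|---|
| 400 | 159.6 | 138.5 | 36% | 46% | 96.9 |
| 300 | 119.7 | 103.8 | 62% | 75% | 72.7 |
| 200 | 79.8 | 69.2 | 95% | 99% | 48.4 |
| 100 | 39.9 | 34.6 | – | – | – |

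The half-width is 1.96 × SE.

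**Step 4: the SD at which the shortfall disappears.** An interaction of 100 calories has 80% power if SD ≤ 100 / (3.228 × √(4/262)) = 250.7. At alpha 0.05 the limit is 288.9.

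**Step 5: sample size, for scale.** At SD 400 and alpha 0.017, 80% power needs about 523 analysable per cell for an interaction of 113 calories and about 668 for 100.

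**Check by simulation.** In 40,000 trials with 262 per cell, SD 400 and alpha 0.017, the interaction was rejected in 1.7% of trials at a true value of 0, 35.6% at 100, 46.1% at 113 and 80.1% at 160.

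**The case against.** The strongest reply is that the power statement contains no error: it names its two groups and the number is right for them. The hypothesis sentence, read without its interaction clause, says that Black adolescents will buy more than White adolescents after congruent ads, which is the 113-calorie contrast. With congruent ads as the reference level, the race coefficient in the planned model equals that contrast. Aim 2 gives a parallel within-arm figure (110 calories), so the choice may be deliberate.

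The within-arm reading is possible, and it is a reason for the plan to name its test. It does not remove the mismatch. The same sentence gives the interaction as the means of judging a differential association, the mediation analysis relies on it, and a non-randomised within-arm contrast cannot answer the Aim 1 question.

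Other points, and what stands of each:
- **The SD of 400 is deliberately conservative.** True. The shortfall against 100 calories holds at SD 400 and 300, but not at 200 or below. The 113 also rests on SD 400, however, so 160 is the like-for-like figure.
- **The target of about 100 calories (about 20%) was set for a between-group difference.** True. The plan states no expected interaction, so 100 and 113 serve only as reference sizes.
- **Alpha 0.017 is not tied to the interaction, and Holm's later steps are less strict.** True. At SD 400 the figure is about 152 at alpha 0.025 and 138 at 0.05, both still above 113.
- **A 95% interval does not match alpha 0.017.** True. The ±97 interval just excludes 100 calories; the interval matching 0.017 is 2.387 × 49.4, or about ±118.
- **A log transformation may be used.** True. The 160 is on the raw calorie scale, as are the plan's 80 and 113.

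**Conclusion.** The concern holds. The plan's one race-related calorie figure for Aim 1 is attached to a contrast other than the interaction that evaluates the race hypothesis. On the plan's own inputs that interaction has 80% power at about 160 calories, not 113. This is 32% of a 500-calorie snack (27% to 40% over the plan's 400 to 600). At SD 400, an interaction estimate of zero would have a 95% interval of about ±97 calories, nearly the size of the plan's target difference.

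The result rests on equal race-by-congruence cells, 9% exclusions, alpha 0.017 applied to the interaction as it is to the two stated figures, and an unadjusted analysis on the raw scale. The factor of 1.41 between the two contrasts does not depend on the SD or on alpha. The size in calories does: about 120 at SD 300, 80 at SD 200 and 40 at SD 100. The main-effect figure of 80 calories is unaffected.

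**What to change.** In Data Analysis, Aim 1:
- **Analysis of primary outcome:** state that the race-by-congruence interaction is the test of the race hypothesis.
- **Power and sample size:** give the interaction's detectable size as the power statement for that hypothesis: 80% power at about 160 calories at SD 400 (about 120 at SD 300, 80 at SD 200), two-sided alpha 0.017, 262 per cell after 9% exclusions. If another alpha is intended for this test, say so and use the matching figure (about 138 at 0.05, SD 400).
- **Interpretation:** add that, at the planning SD of 400, a null interaction is not evidence of equal response in Black and White adolescents.
- **The 113 calories:** keep the figure only as a labelled, non-randomised comparison within the congruent arm.

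The cost is wording. The planned model already contains the interaction, so no new model, alpha change or additional participants are needed. The stated sensitivity for the race hypothesis becomes less favourable. If the authors had meant the within-arm contrast as the test, the change also alters which estimate decides the hypothesis, and they should settle that openly before the data are analysed.

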### Gender of Subjects

We will recruit males and females because research shows pre-adolescent males consume more fast food than females. We will therefore examine differences in responses based on sex. Adjustment of primary analysis will be undertaken to accommodate any imbalances.

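### Aim 2 plans to study who responds more to ads by adjusting for participant characteristics, but an adjustment without a factor-by-condition term estimates who buys more calories, not who responds more

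*Combined protocol and SAP*

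**What the plan says.** The primary model for Aim 2 (Data Analysis) compares the two randomised conditions: "Linear regression will be used to evaluate differences in the mean calories purchased between conditions". To see whether the likes effect differs by race, the plan then names the term it needs: "we will include participant race as a main effect, as well as an interaction term between race and condition". The next sentence turns to other characteristics: "We will also use linear regression to adjust for demographic and behavioral characteristics to investigate how these factors relate to responsiveness to ads". It names no product term, stratified model or subgroup contrast, and it does not list the characteristics.

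Three other places bear on the reading.

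- In Data Analysis, Aim 1, models that control for eating restraint and eating disorder symptoms are given a different purpose: "to examine if those factors affect the number of calories purchased by adolescents".
- Gender of Subjects states: "We will therefore examine differences in responses based on sex". No model for this appears anywhere.
- Two other moderators are planned. One is affective response (Data Analysis, Aim 2, secondary outcomes). The other is awareness of the study's purpose (Methods & Procedure, Aim 3, and Debriefing Procedures). Race is the only factor with an explicit condition interaction term.

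**The concern.** Every Aim 2 participant views food ads, and randomisation is between many and few likes (Methods & Procedure, Aim 2). With no arm free of ads, the design can identify responsiveness in calories purchased only as the difference between the two conditions. A covariate entered without a condition-by-factor term makes that difference the same at every level of the covariate. Its coefficient describes who buys more on average.

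The sentence therefore joins a method to a purpose that the method does not serve. If it is carried out as written, a report could state that boys, older teens or some behavioural group are more responsive to ads when they simply buy more under either condition. A reader could not tell the two apart from the coefficient. The comparison by sex announced in Gender of Subjects also has no model behind it, if it means a difference in ad effect.

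**Working it through.** **Inputs from the plan (Data Analysis, Aim 2).** Alpha: "Using a two-sided Type I error rate of 0.017 to control the experiment-wise error rate at 0.05". Spread: "assuming a SD of 400 calories". Size: "600 in each of two conditions = 1,200 total, not including the 100 pretest participants". Expected exclusions are under 9%; 9% is used here. Analysed: 600 × 0.91 = 546 per condition, or 1,092 in total.

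**Step 1. Reproduce the plan's figures.** Detectable difference = (z for two-sided 0.017 + z for 80% power) × SD × √(1/n₁ + 1/n₂), and the two z values sum to 3.228.

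- Many vs few likes: 3.228 × 400 × √(2/546) = 78 calories, as stated.
- Black vs White adolescents within many likes, 273 each: 3.228 × 400 × √(2/273) = 110 calories, as stated.

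The inputs are therefore the plan's own.

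**Step 2. What the adjusted coefficient estimates.** Take a binary factor split evenly (an assumption). Let d be the difference in mean calories between its two levels under few likes, and δ the difference between levels in the likes effect. With 1:1 allocation, the main-effect coefficient has expectation d + δ/2, and the interaction coefficient has expectation δ. Only the second is responsiveness.

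**Step 3. Illustrations.** The effect sizes are assumptions, not figures from the documents. The standard error of the main-effect coefficient is about 400 × √(2/546) = 24.2.

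| Assumed truth | Main-effect coefficient expects | Significant at 0.017 | Interaction expects | Significant at 0.017 |
|---|---|---|---|---|
| d = 100, δ = 0 (likes effect 78 in everyone) | 100 | about 96% | 0 | 1.4% |
| d = −78, δ = 156 | −78 + 156/2 = 0 | 1.7% | 156 | 81% |
| d = 0, δ = 156 | 0 + 156/2 = 78 | about 80% | 156 | as above |

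The percentages in the first two rows come from simulation with 273 per cell (2,000 trials each). With all 1,200 analysed they become 97% and 1.4% in the first row, and 1.4% and 83% in the second. The first row can be checked by hand: 100/24.2 = 4.13, and 4.13 − 2.387 = 1.74, which gives 96%. In the third row the coefficient expects 78 with the same standard error as the primary contrast, so it has the same power.

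Rows two and three have the same difference in responsiveness. The coefficient is almost never significant in one and usually significant in the other, and the only change is the few-likes means.

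**Step 4. What an interaction model could detect.** For an even split, the standard error is SD × √(4/cell size).

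- Aim 2, 546/2 = 273 per cell: 3.228 × 400 × √(4/273) = 156 calories at alpha 0.017. At alpha 0.05 the multiplier is 1.960 + 0.842 = 2.802, which gives 136.
- Aim 1, 288 × 0.91 = 262 per cell: 3.228 × 400 × √(4/262) = 160 calories.
- Aim 2, assumed 30:70 split: 171 calories at alpha 0.017.
- Power in Aim 2 for a 78-calorie interaction, even split, alpha 0.017: standard error 400 × √(4/273) = 48.4, 78/48.4 = 1.61, and 1.61 − 2.387 = −0.78, which gives 22%.

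**The case against.** The best reply is that the plan nowhere says main effects only. The sentence follows directly on an interaction and states a responsiveness purpose, so it may be underspecified rather than wrong. That stands as a limit: the main-effects reading is inferred. It is still the natural one, because the authors name an interaction for race and speak of moderation for affective response, yet write only of adjustment here.

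A second reply is that responsiveness is never defined, and that Aim 2 may intend what Aim 1 says of its covariate models, namely the link with calories. If so, the method is fine and the wording should change. That also stands, and it is one of the two remedies below.

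Third, Gender of Subjects gives higher fast-food consumption among males as its reason, which is a difference in level, and then moves to adjustment for imbalances. It can be read without any sex-by-condition test.

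A reader might infer more than the documents support:

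- **That a real difference in response would nearly always be missed.** The 1.7% figure needs the few-likes means to offset the effect exactly. With equal few-likes means the coefficient is significant in about 80% of trials, though it still estimates the wrong quantity. The 81% for the interaction is by construction, since 156 is its own 80%-power value.
- **That race is the only moderator in the plan.** Affective response and awareness are planned as moderators too.
- **That the trial's main result is at risk.** The many-versus-few likes comparison and the race interaction do not depend on this sentence.

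**Conclusion.** The point holds for a secondary question. As naturally read, the adjusted models in Aim 2 estimate each characteristic's association with calories averaged over both conditions, and those coefficients cannot be interpreted as responsiveness to ads. A factor with an assumed 100-calorie average shift and no difference in response would be significant in about 96% of trials. When response does differ, what the coefficient shows depends on the few-likes means. Sex and the other characteristics in the sentence have no planned term that could answer the question.

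The 96% rests on the plan's SD of 400, alpha of 0.017 and 9% exclusions, and on an assumed even split. It illustrates the problem and does not predict what the trial will find. The documents do not support saying that the stated question is certain to get a wrong answer: the model is inferred, and it may or may not mislead in a given data set. The primary analysis and the sample size are unaffected.

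**What to change.** Choose one of two changes to Data Analysis, Aim 2.

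**Option 1: answer the responsiveness question.**

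- Prespecify a short list of characteristics that the ads cannot change, for example sex, age and BMI-z, plus any behavioural factor that reflects habits before the study. If behavioural factors measured after ad exposure are left out, say so, because the present sentence covers them.
- For each factor, fit a separate model with condition, the factor and their interaction. Report the interaction estimate with a 95% interval and label it exploratory.
- State the precision. For a binary factor split evenly, 80% power is reached only for a difference in ad effect of about 156 calories in Aim 2 and 160 in Aim 1 at alpha 0.017, or about 136 in Aim 2 at alpha 0.05. These figures do not describe age or BMI-z analysed as continuous variables.
- Clarify Gender of Subjects. If it means differences in ad effect, use the sex-by-condition model in Aim 1 as well. If it means differences in calories purchased, say that.

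**Option 2: keep the adjusted model and change its purpose.** Say that it shows how the characteristics are associated with calories purchased, and claim nothing about responsiveness.

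Neither option needs new data or a larger sample. Option 1 costs a few extra models, and its intervals will be wide. Option 2 costs one sentence and gives up the question.
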